## **1.2 Objective of the Analyses**

The analyses detailed in this document will assess the efficacy and safety of the patients treated with GeneSight guidance in comparison with the patients treated without GeneSight guidance. This analysis plan supersedes the one in the protocol and the previous versions.

## **2 STUDY OBJECTIVES AND DEFINITIONS**

### **2.1 Study Objectives**

#### **2.1.1 Primary Objective**

The primary objective of this study is to evaluate the impact of GeneSight Psychotropic on response to psychotropic treatment as judged by the mean percentage change in the 17-item Hamilton Depression (HAM-D17) score from baseline to end of Week 8 of the study.

H0: There is no difference in mean percentage change from baseline in HAM-D17 between GeneSight (GEN) and Treatment As Usual (TAU) at Week 8

Ha: The mean percentage change from baseline in HAM-D17 for GEN is different from TAU at Week 8

#### **2.1.2 Secondary Objectives**

*The following secondary analyses will be performed in order of appearance.*

##### **2.1.2.1 Evaluate the following for GEN vs TAU:**

- Percentage of responders in HAM-D17 at Week 8 in each treatment group (see definition in 7.1)
- Percentage of remitters in HAM-D17 at Week 8 in each treatment group (see definition in 7.2)

##### **2.1.2.2 Evaluate the following for GEN vs E-GEN:**

- Mean percentage change from baseline in HAM-D17 at Week 8
- Percentage of responders in HAM-D17 at Week 8
- Percentage of remitters in HAM-D17 at Week 8

**The treatment groups used for all subsequent analyses (all scales at each time point) will depend on the results in 2.1.2.2**

- If GEN is not statistically different than E-GEN at any endpoint, GEN and E-GEN treatment arms will be combined and compared to TAU
- If E-GEN is statistically superior to GEN at any endpoint, E-GEN will be compared to TAU
- If GEN is statistically superior to E-GEN at any endpoint, GEN will be compared to TAU

### **2.1.2.3 The subsequent secondary objectives are to evaluate the following for treatment groups determined in 2.1.2.2:**

- Mean percentage change in HAM-D6 (see definition in 7.3) from baseline to Week 8;
- Mean percentage change in the 16-item Quick Inventory of Depression Symptomology (QIDS-SR16) from baseline to Week 8;
- Mean percentage change in the 9-item Patient Health Questionnaire (PHQ-9) from baseline to Week;
- Percentage of responders at Week 8 in each treatment group on the HAM-D6, QIDS-SR16, PHQ-9 (see definition in 7.1);
- Percentage of remitters at Week 8 in each treatment group on the HAM-D6, QIDS-SR16, and PHQ-9(see definition in 7.2)

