4.0 OBJECTIVES

4.1 Hypothesis

GEN and E-GEN reduces MDD symptoms and is more cost-effective than TAU for patients suffering from MDD and having had – within the current episode – an inadequate response to at least one psychotropic medication included in GEN. Furthermore, E-GEN improves predictions of patients’ clinical responses and provides greater clinical utility as compared to GEN.

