10.0 SAMPLE SIZE

The study will recruit participants from approximately 8-12 sites stratified into 2 clusters. CAMH will constitute one study site and a single stratified cluster. The remaining sites will constitute the second cluster. The sample size required for this study was calculated using effect size estimates drawn from a previous study conducted by Hall-Flavin et al.(11) Assuming an effect size of 0.30 in HAM-D₁₇ score favoring the treatment group, intra class coefficient between clusters of 20%, statistical power of 90%, an alpha level of 0.05, and an expected 16.7% rate of premature discontinuation (based on ongoing studies and experience with the intervention) by Week 8 (primary endpoint), a total of 570 participants (i.e., 190 per treatment arm) are required to detect the same effect in this study. Sample size calculations were determined using SAS (SAS Institute, Inc., Version 9.3, Cary, NC).

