16.1.6 Decision Rule

An overall alpha-level of 0.05 will be used to determine statistical significance and all statistical tests will be two-sided. All data will be analyzed using SAS (SAS Institute, Inc., Version 9.3, Cary, NC).

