### **2.1.3 Long-term Secondary Objectives**

The long-term secondary objectives are to evaluate the following for treatment groups determined from results of 2.1.2.2:

- Mean percentage change in HAM-D17, HAM-D6, QIDS-SR16, PHQ-9, from baseline to Week 12, Month 6, Month 9, Month 12, (across all scales, where applicable) in each treatment group;
- Percentage of responders at Week 12, Month 6, Month 9, and Month 12 in each treatment group on the HAM-D17, HAM-D6, QIDS-SR16, PHQ-9, (across all scales, where applicable) (see definition in 7.1);
- Percentage of remitters at Week 12, month 6, month 9, and month 12 in each treatment group on the HAM-D17, HAM-D6, QIDS-SR16, PHQ-9 (across all scales, where applicable) (see definition in 7.2);

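### The SAP does not list E-GEN, or GEN and E-GEN pooled, against TAU on HAM-D17 at Week 8, although the protocol sets out E-GEN against TAU

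*SAP*

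**What the plan says.** SAP 1.2 states that the SAP replaces the analysis plan in the protocol. Its comparisons run as follows.

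- **2.1.1 (primary):** GEN against TAU, HAM-D17 percentage change at Week 8.
- **2.1.2.1:** GEN against TAU, HAM-D17 response and remission at Week 8.
- **2.1.2.2:** GEN against E-GEN on the same three Week 8 HAM-D17 endpoints. The result decides which arms meet TAU afterwards. The first branch reads "If GEN is not statistically different than E-GEN at any endpoint, GEN and E-GEN treatment arms will be combined and compared to TAU". In the other two, whichever test arm is superior goes forward alone. A parenthesis says the rule covers every scale and visit in the later analyses.
- **2.1.2.3:** "The subsequent secondary objectives are to evaluate the following for treatment groups determined in 2.1.2.2". The Week 8 items are change, response and remission on HAM-D6, QIDS-SR16 and PHQ-9.
- **2.1.3:** HAM-D17 reappears here, at later visits: "Mean percentage change in HAM-D17, HAM-D6, QIDS-SR16, PHQ-9, from baseline to Week 12, Month 6, Month 9, Month 12".

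The protocol is wider. Section 4.1 states "GEN and E-GEN reduces MDD symptoms and is more cost-effective than TAU for patients suffering from MDD". Section 4.3 compares all three arms on symptoms, response and remission. Section 16.1.3 includes an alternative in which mean HAM-D17 improvement with E-GEN exceeds that with TAU, using the 8-week score. Section 16.1.4 plans relative risks of response and remission for each test arm with TAU as referent.

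**The concern.** E-GEN is a randomised arm with its own hypothesis against TAU, yet the SAP lists no such comparison on the main outcome at the main time point. The protocol's version of it (16.1.3 and 16.1.4) falls away when the SAP takes over, and nothing replaces it or explains the omission.

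Two practical consequences follow.

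- **Mixed arms at one visit.** HAM-D6 is six of the HAM-D17 items (SAP 7.3). If the arms are pooled, HAM-D6 at Week 8 compares two arms with TAU while HAM-D17 at Week 8 compares one. A positive HAM-D6 beside an inconclusive HAM-D17 could then partly reflect patient numbers.
- **Mixed arms over time.** Unless GEN is selected, the arms behind the HAM-D17 comparison with TAU change between Week 8 and Week 12, so the two results do not describe the same contrast.

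SAP 1.1 says the results go to a health technology application, where readers will look for each test arm against usual care.

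**Working it through.** **1. Week 8 HAM-D17 contrasts as listed**

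| Contrast | Place in the SAP |
|---|---|
| GEN vs TAU, change | 2.1.1 |
| GEN vs TAU, response and remission | 2.1.2.1 |
| GEN vs E-GEN, all three endpoints | 2.1.2.2 |
| E-GEN vs TAU | not listed |
| GEN+E-GEN vs TAU | not listed |

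**2. What each branch of 2.1.2.2 delivers against TAU**

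| Result of 2.1.2.2 | Week 8 HAM-D6, QIDS-SR16, PHQ-9 | Week 8 HAM-D17 as listed | Added if the parenthesis covers Week 8 HAM-D17 | HAM-D17 from Week 12 |
|---|---|---|---|---|
| No difference | pooled | GEN | pooled | pooled |
| E-GEN superior | E-GEN | GEN | E-GEN | E-GEN |
| GEN superior | GEN | GEN | nothing new | GEN |

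On the broadest reading, E-GEN alone meets TAU in one branch of three.

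**3. Inputs**

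From Protocol 10.0:
- standardised effect 0.30;
- "statistical power of 90%, an alpha level of 0.05";
- an intraclass coefficient of 20%;
- 16.7% loss by Week 8;
- 190 per arm, 570 in all.

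From Protocol 16.1.6: "all statistical tests will be two-sided". SAP 6 also says two-sided 0.05.

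**4. The plan's own figure**

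Two-sided, ignoring the intraclass coefficient: n = 2 × (1.960 + 1.282)² / 0.30² = 233.5, so 234 per arm. After loss, 234 / 0.833 = 280.9, so 281 per arm and 843 in all. The stated 570 is not reproduced. The protocol does not say how the coefficient was used. If it cut the variance by 20% (an assumption), the need is 188 evaluable and 226 after loss. This is a separate matter, and I take 190 per arm as given below.

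**5. Power at the planned size**

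Evaluable per arm: 190 × 0.833 = 158. Outside every listed Week 8 HAM-D17 comparison with TAU: 190 / 570 = 33.3%.

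In SD units, SE = √(1/n₁ + 1/n₂) and power ≈ Φ(d/SE − 1.960).

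- One arm vs TAU, 158 vs 158: SE = √(2/158) = 0.1125; 0.30/0.1125 = 2.667; Φ(0.707) = 76.0%.
- Pooled vs TAU, 316 vs 158: SE = √(1/316 + 1/158) = 0.0974; 0.30/0.0974 = 3.079; Φ(1.119) = 86.8%.
- SE ratio: 0.0974 / 0.1125 = 0.866, about 13% smaller.

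**6. Range**

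| Assumption (same effect in both test arms) | One arm vs TAU | Pooled vs TAU |
|---|---|---|
| d = 0.20, 158 per arm | 42.8% | 53.7% |
| d = 0.25, 158 per arm | 60.3% | 72.8% |
| d = 0.35, 158 per arm | 87.5% | 94.9% |
| d = 0.40, 158 per arm | 94.5% | 98.4% |
| d = 0.30, no loss (190 per arm) | 83.2% | 92.2% |
| d = 0.30, 158 per arm, variance × 0.8 | 84.6% | 93.1% |

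The gain depends on similar effects. If GEN has 0.30 and E-GEN 0.20, the pooled effect is (0.30 + 0.20)/2 = 0.25, and pooled power is 72.8%, below the 76.0% for GEN alone.

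**The case against.** **The SAP may already allow the comparison.** The parenthesis in 2.1.2.2 can be read to include HAM-D17 at Week 8. SAP 5.2 re-runs the primary-endpoint model with more covariates, and analyses HAM-D17 response and remission by visit, without naming arms. This stands to the extent that a reader may not infer that the SAP excludes any such analysis. It is silent or ambiguous. But secondary analyses follow the order in which they appear (2.1.2), and an unlisted one has no position. The broad reading also leaves out E-GEN alone in two branches of three.

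**The data will be shown anyway.** SAP 4 calls for tables with all three arms and an effect-size column. It does not say which contrast that column holds. If all arms are in one model, a point estimate for E-GEN vs TAU follows by subtracting GEN vs E-GEN from GEN vs TAU. Its confidence interval does not, because the two contrasts share the GEN arm.

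**A reader might infer that a third of the patients are wasted.** The documents do not support that. E-GEN against GEN is the protocol's second primary objective (4.2), and SAP 2.1.2.2 tests it on HAM-D17 at Week 8. E-GEN adds only weight-gain markers to GEN (Protocol 3.3), so GEN is a natural comparator. SAP 5.1 does not say how many arms the model includes. If three, E-GEN patients also inform the baseline slope and covariance.

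**A reader might take 76% against 87% as power lost by the primary test.** It is not. The higher figure belongs to a different, secondary contrast. E-GEN vs TAU alone would have the same 76% at d = 0.30.

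**The HAM-D6 mismatch is conditional.** HAM-D6 gains numbers only if the arms are pooled, and the two scales can differ for reasons other than sample size.

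**Testing HAM-D17 once against TAU and then moving to other scales is coherent.** As a testing strategy, yes. It still leaves a hypothesis in Protocol 4.1 without a listed estimate at Week 8.

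**Conclusion.** The point holds as a gap in what the SAP lists. It should be fixed, but it does not threaten the primary analysis: the GEN vs TAU estimate, test and error rate are unaffected.

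Followed as written, the SAP gives no E-GEN vs TAU result on Week 8 HAM-D17. The most generous reading gives one only if E-GEN is superior to GEN. At d = 0.30 in both test arms, the pooled secondary contrast would have about 87% power and a standard error 13% smaller than a single arm vs TAU at 76%.

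Those figures rest on 158 evaluable per arm (dropout only) and ignore the intraclass coefficient. They come before per-protocol exclusions, although SAP 3.4 draws the main conclusion in the per-protocol population, so absolute power is likely lower there. The 0.866 ratio needs only equal arm sizes and a common variance.

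**What to change.** Keep GEN vs TAU as the primary test, with its power unchanged. In SAP 2.1.2.3, add an item exempt from the arm-selection rule, along these lines:

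*For HAM-D17 percentage change, response and remission at Week 8, the contrasts (a) E-GEN vs TAU and (b) GEN+E-GEN vs TAU will be estimated from models fitted to all three arms and reported whatever the result of 2.1.2.2.*

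Then settle three details:

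- **Place in the order.** Either give the six results (three endpoints × two contrasts) a fixed position, or report them as estimates with 95% confidence intervals outside the formal order. The second choice displaces none of the listed secondary tests. SAP 6 gives no multiplicity rule beyond two-sided 0.05, so the choice must be written down.
- **Scope of the rule.** State whether the parenthesis in 2.1.2.2 is meant to include Week 8 HAM-D17.
- **Model.** State in 5.1 and 5.2 which arms are fitted, including for the primary test.

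The cost is a short SAP amendment and extra contrasts from model types already planned, with no new data. The downside is six more secondary results to report. The pooled one averages two effects and should be read beside the separate contrasts if GEN and E-GEN differ.

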### **2.1.3 Long-term Secondary Objectives**

The long-term secondary objectives are to evaluate the following for treatment groups determined from results of 2.1.2.2:

- Mean percentage change in HAM-D17, HAM-D6, QIDS-SR16, PHQ-9, from baseline to Week 12, Month 6, Month 9, Month 12, (across all scales, where applicable) in each treatment group;
- Percentage of responders at Week 12, Month 6, Month 9, and Month 12 in each treatment group on the HAM-D17, HAM-D6, QIDS-SR16, PHQ-9, (across all scales, where applicable) (see definition in 7.1);
- Percentage of remitters at Week 12, month 6, month 9, and month 12 in each treatment group on the HAM-D17, HAM-D6, QIDS-SR16, PHQ-9 (across all scales, where applicable) (see definition in 7.2);

### **2.1.4 Exploratory, Safety, and Tolerability Objectives**

- Mean percentage change in Generalized Anxiety Disorder 7-item (GAD-7) scale from baseline to end of Week 8, Week 12, Month 6, Month 9, Month 12;
- Percentage of responders and remitters at Week 8, Week 12, Month 6, Month 9, Month 12 on GAD-7 (see definition in 7.1 and 7.2);
- Change in SF-36 from baseline to end of Week 12, Month 6, Month 9, and Month 12;
- Percentage of responders at Week 12, Month 6, and Month 12 on SF-36 (see definition in 7.1);
- Mean percentage change in the Clinical Global Impression: Severity of Illness (CGI-S) from baseline to end of Week 12 and Month 12;
- Percentage of responders and remitters at Week 12 and Month 12 on CGI-S in each treatment group (see definition in 7.1 and 7.2);

- Percentage responders at Week 12 and Month 12 on CGI-I (Clinical Global Impression: Global Improvement) in each treatment group (see definition in 7.1);
- Percentage responders at Week 12 and Month 12 on CGI-IE (Clinical Global Impression: Efficacy Index) in each treatment group (see definition in 7.1);
- Compare congruence of medications between treatment groups at Week 8, Week 12, Month 6, Month 9, and Month 12 (see 7.5 for definition);
- Percentage of subjects who experienced adverse events (AE) at Week 8, Week 12, and Month 12;
- Change in Udvalg for Kliniske Undersogeler (UKU) side effect rating scale; Frequency, Intensity and Burden of Side Effects Ratings (FIBSER); and weight gain from baseline to Week 8, Week 12, and Month 12;
- Percentage of patients compliant with medications at Week 8, Week 12, Month 6, Month 9, and Month 12 between treatment groups using Brief Adherence Rating Scale (BARS) and prescription filling data

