16.1.3 Continuous Outcomes

If the HAM-D₁₇ scores from baseline to end of Week 8 of the study meet the assumptions of ANOVA modeling, repeated-measure (i.e., mixed) ANOVA models will be used to model the outcome scores over time. This model accounts for a between-group and within-individual effect, which allows for the examination of average differences between groups while also accounting for the correlation between participant scores between each measurement. If the HAM-D₁₇ scores do not meet standard ANOVA assumptions, GEEs will be used to model repeated measurements of outcome scores over time, as these models are more robust to departures from the standard assumptions and also allow the investigator to specify the correlation structure of the repeated measurements. Mean symptom improvement for all continuous measures (i.e., depression scales) will be calculated using the standard formula $(\frac{y_2 - y_1}{y_1}) * 100$, where y_1 is the baseline score for each participant for each rating scale and y_2 is the 8 week score for each participant for each rating scale.

Two hypotheses related to the primary objectives will be tested, where μ_1 is the mean HAM-D₁₇ % symptom improvement in the GEN group, μ_2 is the mean HAM-D₁₇ % symptom improvement in the E-GEN group and μ_3 is the mean HAM-D₁₇ % symptom improvement in the TAU group.

Primary objective (1):

$$H_0: \mu_1 = \mu_2 = \mu_3$$

$$H_a: \mu_1 = \mu_2 > \mu_3$$

Primary objective (2):

$$H_0: \mu_1 = \mu_2 = \mu_3$$

$$H_a: \mu_1 < \mu_2 > \mu_3$$

For all continuous measures, a responder will be defined as a participant with 50% change from baseline in total scale score. Remitters at week 8 and at week 12 will be defined as HAM-D₁₇ ≤7 in each treatment group. Differential time to response/remission of depressive symptoms over 8 and 12 weeks will be plotted using Kaplan-Meier curves and Cox proportional hazard models will test the null hypothesis of no difference in time to response/remission between groups.

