APPENDIX VI: Clinical Global Impression (CGI)

1. SEVERITY OF ILLNESS (CGI-S)

Considering your total clinical experience with this particular population, how ill is the patient at this time?

- | | |
|-----------------------------|---|
| 0 = Not assessed | 4 = Moderately ill |
| 1 = Normal, not at all ill | 5 = Markedly ill |
| 2 = Borderline mentally ill | 6 = Severely ill |
| 3 = Mildly ill | 7 = Among the most extremely ill patients |

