### **2.2.3 Exploratory, Safety, and Tolerability Variables**

- Percentage change in GAD-7
- Percentage change in CGI-S
- Change in SF-36
- Responders of GAD-7, CGI-S, CGI-I, CGI-EI, and SF-36
- Remitters of GAD-7, and CGI-S
- Change in EuroQol (EQ-5D-5L)
- Change in BARS
- Percentage of patients on congruent medications
- Prescription filling frequency between study visits
- Number of Adverse Events (AE)
- Change in UKU

- Change in FIBSER

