### **5.2 Secondary & Exploratory Efficacy Analyses**

The secondary analyses will be conducted using MMRM method for continuous response variables and ANCOVA with robust regression for complete cases for the PP population and may also be conducted for the ITT population.

As a secondary analysis, the following covariates will be added to the primary endpoint model with baseline score and analyzed the same way: treatment, age, gender, site type, and race included in the model. If covariates are not statistically significant, they may be dropped from the final model.

The secondary and exploratory measures of efficacy including percentage change from baseline in HAM-D6, QIDS-SR16, PHQ-9, GAD-7, CGI-S, change in EuroQol (EQ-5D-5L), and change in SF-36 will be analyzed the same way as for the primary efficacy variable above with baseline score included in the model. The secondary measures of efficacy will also be analyzed with baseline score, treatment, gender, site type, age, and race included in the model. If covariates are not statistically significant, they may be dropped from the final model.

Percentage of responders for HAM-D17, HAM-D6, QIDS-SR16, PHQ-9, GAD-7, CGI-S, CGI-I, CGI-EI, and SF-36, and remitters for HAM-D17, HAM-D6, QIDS-SR16, PHQ-9, GAD-7, and CGI-S will be analyzed by visit, separately, using a Generalized Linear Mixed model. Pre-specified covariates may be added.

Percentage of patients on congruent and incongruent medications will be compared between GEN and TAU using Chi-square tests at each time point.

Medication compliance using BARS and prescription filling data will be summarized and compared between treatment groups (see 7.6 for description).

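### CGI-S is planned as percentage change from baseline, but its floor is 1 rather than 0, so the reported percentage understates improvement; change in points would be better

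*SAP*

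**What the plan says.** SAP 2.1.4 sets as an exploratory objective "Mean percentage change in the Clinical Global Impression: Severity of Illness (CGI-S) from baseline to end of Week 12 and Month 12". SAP 2.2.3 repeats it in the variable list as "Percentage change in CGI-S". SAP 5.2 then groups the scale with two others: "CGI-S, change in EuroQol (EQ-5D-5L), and change in SF-36 will be analyzed the same way as for the primary efficacy variable above", with the baseline score in the model.

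Protocol Appendix VI anchors the scale. The best rating is "1 = Normal, not at all ill", the next is "2 = Borderline mentally ill", and the worst is "7 = Among the most extremely ill patients". The remaining code is "0 = Not assessed", which records a missing assessment and is not a level of illness.

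The SAP gives no formula for percentage change. The only one in the documents is in protocol 16.1.3, (y2 - y1)/y1 x 100, where y1 "is the baseline score for each participant for each rating scale". Neither document rescales CGI-S before the percentage is taken.

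Elsewhere the SAP handles CGI-S in absolute terms. Under 7.1 a responder is a patient who falls by at least one category, whereas the depression scales use a 50% decrease. Under 7.2 a remitter is a patient at the floor. SF-36, EQ-5D-5L, UKU and FIBSER are listed in 2.2.3 as plain change.

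**The concern.** A percentage change is easiest to interpret when zero on the scale means that none of the measured quantity is present. HAM-D17 items start at 0 (protocol Appendix II), QIDS-SR16 runs from 0 to 27 (Appendix III) and PHQ-9 from 0 to 27 (protocol 8.2.1). On those scales complete absence of symptoms gives -100%. On CGI-S a patient rated normal still scores 1, so dividing by the raw baseline treats a well patient as retaining 1/B of the illness.

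At stake is how one exploratory estimate is read. A mean CGI-S percentage improvement would look smaller than the clinical change that it summarises. The coarse seven-category scale also makes the weight of a single step depend visibly on the starting category.

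**Working it through.** The plan states no figure for CGI-S percentage change, so there is nothing to reproduce. The check applies the protocol 16.1.3 formula to the Appendix VI anchors. That formula is written for week 8 and SAP 1.2 says that the SAP supersedes the protocol's analysis plan, so using it for CGI-S at Week 12 and Month 12 is an inference. It is the ordinary meaning of the term, and the documents offer no other.

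**Shortfall.** For a patient moving from B to y, the literal improvement is (B - y)/B. Measured against the distance to the floor it is (B - y)/(B - 1). The first divided by the second is (B - 1)/B, so the literal figure falls short by 1/B whatever y is.

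**Full recovery and one step.** Recovery to 1 gives (1 - B)/B; a one-point gain has size 1/B.

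| Baseline B | Recovery to 1 | One-point gain | Shortfall 1/B |
|---|---|---|---|
| 2 | -50.0% | 50.0% | 50.0% |
| 3 | -66.7% | 33.3% | 33.3% |
| 4 | -75.0% | 25.0% | 25.0% |
| 5 | -80.0% | 20.0% | 20.0% |
| 6 | -83.3% | 16.7% | 16.7% |
| 7 | -85.7% | 14.3% | 14.3% |

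No valid rating gives -100%.

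**Dependence on the assumed baseline range.** The documents give no CGI-S entry threshold. Protocol 1.5 describes the population as having moderate to severe MDD on QIDS, so the range is an assumption. The step ratio is the highest baseline divided by the lowest.

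| Baselines | Full recovery reads as | Step ratio |
|---|---|---|
| 4 to 6 | 75.0% to 83.3% | 6/4 = 1.50 |
| 4 to 7 | 75.0% to 85.7% | 7/4 = 1.75 |
| 3 to 7 | 66.7% to 85.7% | 7/3 = 2.33 |
| 2 to 7 | 50.0% to 85.7% | 7/2 = 3.50 |

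**Ranking.** Even within 4 to 7 the order of two improvements can reverse. From 4 to 2 (two points) is -2/4 = -50.0%; from 7 to 4 (three points) is -3/7 = -42.9%.

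**Which part is specific to CGI-S.** One HAM-D17 point is 1/14 = 7.1% from 14 (the per-protocol minimum in SAP 3.2.1) and 1/28 = 3.6% from an illustrative 28, a twofold difference. Unequal weighting by baseline is therefore a property of percentage change in general.

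**Candidate remedies.** With change in points, a step counts the same at every baseline (ratio 1.0). With a percentage taken on (CGI-S - 1), a step is 1/(B - 1). Over baselines 4 to 7 that is 33.3% against 16.7%, a ratio of 2.0; over 2 to 7 it is 100% against 16.7%, a ratio of 6.0. That version is undefined at baseline 1.

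**The case against.** The strongest reply is that this changes little. CGI-S is exploratory and is not collected at week 8, the primary time point. Baseline score is already in the model. Response and remission on CGI-S are defined in absolute terms, so readers will also have results that respect the floor. Randomisation should make the baseline mix similar across arms, so the shrinkage is similar in each. All of this stands, and it limits the point to the continuous estimate and its interpretation. It does not remove the point: a baseline covariate does not give the scale a meaningful zero, and the responder and remitter analyses do not correct the mean.

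A reader might infer more than the documents support:

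- **That recovery reads as only 50% and steps differ 3.5-fold.** Both need a baseline of 2, "2 = Borderline mentally ill". No criterion excludes it, but it is unlikely in moderate to severe MDD. These figures are the theoretical extreme.
- **That CGI-S remitters will look worse than HAM-D17 remitters.** HAM-D17 remission in SAP 7.2 is a score of 7 or less, not zero. From 14 to 7 is -50% and from 28 to 7 is -75%, while a CGI-S remitter from 4 shows -75%. Only the attainable maximum differs.
- **That CGI-S and HAM-D17 percentages will stand side by side in one table.** SAP section 4 sets table columns by arm and does not say this.

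**Conclusion.** The point holds as a minor one. Percentage change suits CGI-S poorly because the scale has no zero severity level. The literal figure is (B-1)/B of the improvement measured to the floor: 25% too low at a baseline of 4, and 14% too low at 7. On the assumption that baselines are mostly 4 to 7, full recovery reads as -75% to -86%, and one point is worth 1.75 times as much at the lower end as at the upper.

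This rests on dividing by the raw baseline, as in protocol 16.1.3, and on the assumed baseline range. The non-zero floor and the seven-category scale are what set CGI-S apart; unequal weighting alone would apply equally to HAM-D17. It would be wrong to infer that the arm comparison is biased. The p-value should be little affected, though this is reasoned from randomisation and was not simulated. The primary result is not touched.

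**What to change.** In SAP 2.1.4, 2.2.3 and 5.2, replace percentage change in CGI-S with change from baseline in CGI-S points, and keep baseline CGI-S as the covariate. SF-36 and EQ-5D-5L are already handled in this way, and it matches the absolute one-category response rule in SAP 7.1. Do not substitute a percentage computed on (CGI-S - 1): it repairs the floor but widens the step imbalance and fails at a baseline of 1.

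The cost is SAP wording and one derived variable, with no new data. The drawback is that CGI-S would no longer carry the same unit label as the depression scales.
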